8.2.6.2. Exclusion Criteria

Patients will be excluded from the study if they meet any of the following criteria:

- Noted development of FVIII inhibitors in the data source any time before index date or fulfilling any of the following criteria of a previously developed algorithm (Batt et al., 2022):
 - Treatment with bypassing agents, such as aPCC or recombinant activated FVII (rFVIIa), at any time prior to the index date.
 - Treatment with rituximab at any time prior to the index date, this criterion would not apply if it was noted in the data source that it was used for another indication, e.g., treatment of lymphoma.
 - Noted use of assay to measure FVIII inhibitors (Duncan et al., 2013) and high dose of FVIII use at any time prior to the index date that is in line with immune tolerance induction. The exact definition of dosage in line with immune tolerance induction will be further defined in the statistical analysis plan (SAP) and may be data source specific.
- Treated with emicizumab at any time prior to the index date.

These criteria will ensure that the patient is eligible for the extended indication of emicizumab.

8.3. VARIABLES

A feasibility assessment was conducted between April 2023 and October 2023 to provide input on the availability of the variables in the data sources, the results from the feasibility are detailed in the respective sections. Given that availability of variables varies across registries some variable might require variable derivation. A detailed specification of the operationalisation of all variables will be given in the SAP. A summary of the variables of the study is given in Table 2.

Table 2. Summary list of variables.

Section	Variables	Described in section
Inclusion and exclusion	Diagnosis of congenital HA	8.2.6.1.
criteria	FVIII level	8.2.6.2.
	FVIII inhibitor status	
	Severe bleeding phenotype	
	Initiation of emicizumab treatment	
	Previous treatment with emicizumab	
Exposure	Emicizumab treatment:	8.3.2.2.
	o Start date	
	 Stop date 	
	o Dose	
	o Frequency	
	 Reason for treatment 	
	 Length of treatment 	
	 Reason for discontinuation 	
Censoring variables	Date of death.	8.2.5.
	 End of observation, e.g., due to loss to follow-up, emigration, or disenrollment from the registry. 	
	 Date of emicizumab treatment discontinuation. 	
Safety variables	SAEs	8.3.1. 8.3.2.1.
	 Number of events 	
	o Diagnosis	
	 Start date 	
	o Outcome	
	 Relatedness to treatment 	
	 Treatment of SAE 	
	TE events	
	 Number of events 	
	o Diagnosis	
	 Start date 	
	o Outcome	
	 Relatedness to treatment 	

Hemlibra—F. Hoffmann-La Roche Ltd Protocol BO44691, Version 2.0

Section	Variables	Described in section
	 Treatment of TE event 	
	• TMA	
	 Number of events 	
	o Diagnosis	
	o Start date	
	o Outcome	
	 Relatedness to treatment 	
	 Treatment of TMA event 	
	 Serious systemic hypersensitivity reactions, including anaphylaxis 	
	 Number of events 	
	o Diagnosis	
	o Start date	
	o Outcome	
	 Relatedness to treatment 	
	 Treatment of serious systemic hypersensitivity reaction 	
Patient's demographic	• Age	8.3.2.3.
characteristics	• Sex	
	Ethnicity	
	Weight	
	Height	
	Country of residence	
Patient's haemophilia	Date of diagnosis of congenital HA	8.3.2.3.
related characteristics	Any major complications:	
	o Bleeding	
	o Hemarthrosis	
	 Infections from injections 	
	Prior treatments for haemophilia	

Hemlibra—F. Hoffmann-La Roche Ltd Protocol BO44691, Version 2.0

Section	Variables	Described in section
Medical history	Concomitant medications	8.3.2.3.
	o Start date	
	o End date	
	Other medical history and concurrent conditions	
Risk factors for TE events	 Known risk factors for TE events (see details below) 	8.3.2.4.

HA, Haemophilia A; TE, Thromboembolic; TMA, Thrombotic Microangiopathy; FVIII, Coagulation Factor VIII; SAE, Serious Adverse Event.

8.3.1. Primary and Secondary Safety Variables

The primary safety variable is TE events as recorded in the data source.

The secondary safety variables are:

- TMA
- Serious systemic hypersensitivity reactions, including anaphylaxis
- SAEs (for definition of SAEs see section 10.1.2.)

The relationship to the treatment will be detailed according to available information in each registry. If this is not available in the registry, time to the first primary or secondary safety events will be described, for further details see section 8.7.

The reporting of AEs in the considered registers for further engagement differs, an overview is given in Table 3 and the details are provided below.

Table 3.	Reporting	of adverse	events among	the considered	data sources.
			U		

Data source	Country	Coding standard
UKNHD	UK	Local adaptation of EUHASS
FranceCoag	France	EUHASS (ICD-10 used for further classification of malignant disorders)
HemoNED	Netherlands	EUHASS
ATHNdataset	US	SNOMED, MedDRA
WBDR	Multi-country	Standardised module
CBDR	Canada	CHESS

UKNHD, UK National haemophilia database; **UK**, United Kingdom; **EUHASS**, European Haemophilia Safety Surveillance; **ATHNdataset**, American Thrombosis and Hemostasis Network; **US**; United States; SNOMED **CT**, Systemized Nomenclature of Medicine – Clinical Terms; **MedDRA**, Medical Dictionary For Regulatory Activities; **WBDR**, World Bleeding Disorders Registry; **CBDR**, Canadian Bleeding Disorders Registry; **CHESS**, Canadian Hemophilia Surveillance System; **ICD**, International Classification Of Diseases.

The European Haemophila Safety Surveillance (EUHASS) system is a pharmacovigilance program that aims to monitor the safety of treatments for patients with haemophilia and other inherited bleeding disorders in Europe through a prospective AE reporting system. The program started in October 2008 and includes participating centres located across more than 30 European countries. The following events are reported to EUHASS either as they occur or as a minimum at the end of every 3-month surveillance period (European Haemophilia Safety Surveillance, n.d.):

- Acute or allergic events
- Transfusion-transmitted infections
- Inhibitors
- Thromboses
- Malignancies
- New cardiovascular events
- Neurological events
- Unexpected Poor Efficacy
- Other AE Possibly Related to Concentrate
- Deaths

For each event reported, data are collected on the patient's age, diagnosis and severity; as well as details about the product and batch numbers involved; and finally details about the event outcome and presence of other risk factors (Makris et al., 2011). Event-specific data are submitted anonymously using the Soundex coding system to avoid

Hemlibra—F. Hoffmann-La Roche Ltd

Protocol BO44691, Version 2.0

duplicate reporting. EUHASS data are not collected according to the medical dictionary for regulatory activities (MedDRA) classifications; however, AEs have been previously aligned to MedDRA preferred terms.

For the UKNHD data source, event reporting has been harmonised with the EUHASS program, and any reported event from participating centres are anonymised and automatically forwarded to EUHASS by the National Haemophilia Database (NHD). Yet, whenever a new inhibitor is reported, the UK Haemophilia Centre Doctors' Organisation (UKHCDO) requests more detailed information, which is not passed onto EUHASS. The additional data requested by the UKHCDO when a new inhibitor is reported include (World Federation of Hemophilia, 2009):

- Coagulation disorder, severity, and genotype if known
- Any relatives with inhibitors
- First inhibitor detection date and the reason for the test
- Inhibitor value at first detection and maximum value
- Any change in the value of factor VIII- or factor IX-coagulant (FVIII:C or FIX:C)
- Any change in bleeding pattern
- Treatment protocol before inhibitor development
- Time in chronological and exposure days from first dose to inhibitor development

The Canadian Hemophilia Surveillance System (CHESS) uses the same methodology as the EUHASS program (Dolan et al., 2014).

For the WBDR data source, an AE module is available at both baseline (when the patient enrolled in the registry) and follow-up visits. When an AE is reported, the participant centre must complete the following fields:

- Start date of onset (i.e., the date the patient first experiences the AE)
- Events (Infection, allergic reaction including anaphylaxis, TE event, TMA, lack of efficacy, injection site reaction or other event)
- Date of resolution (i.e., the date by when the patient stops experiencing the AE)
- Interventions

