6.2. RATIONALE

The marketing authorisation holder (MAH) submitted extension of indication for Hemlibra to include routine prophylaxis of bleeding episodes in patients with congenital HA without FVIII inhibitors who have moderate disease ($1\% \le FVIII \le 5\%$) with severe bleeding phenotype.

Hemlibra—F. Hoffmann-La Roche Ltd Protocol BO44691, Version 2.0

On 15 December 2022, the CHMP issued a positive opinion for this new extension of indication; the European Commission (EC) decision was received on 23 January 2023.

To fulfil the category 3 post-authorisation safety study (PASS) regulatory commitment in the EU, the MAH proposed a multi-registry, non-interventional (NI) PASS to characterise the important potential risk of thromboembolic (TE) events (not associated with aPCC exposure) specifically and inform on the long-term safety profile of emicizumab in the new patient population.

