8.3.2.2. Exposure Definition

Exposure will be based on dates of prescriptions and dispenses, and details on the numbers of prescriptions and doses, as reported in the data source. The start of exposure (index date) is defined as the first prescription or injection of emicizumab, as noted in the data source. An overview of the variables available to define exposure during follow-up can be seen in Table 4. All registers cover the haemophilia related treatments: emicizumab, aPCC, Eptacog alfa (activated), and Factor VIII transfusions.

If the registry does not include information on exact stop dates of treatment exposure, as in the case of HemoNED, treatment will be considered ongoing for as long as new prescriptions, injections or dispenses are noted in the data source and are consistent with continuous treatment. To accommodate non-perfect adherence or other situations where the series of prescriptions are part of a continuous exposure period, an additional 90 days will be added to exposure period, at the last noted injection or at the end of prescribed supply, corresponding to 3 times the half-life of emicizumab when the patient will be considered no longer affected by the drug (Hallare and Gerriets, 2023). If the patient has not filled another prescription or received an injection at the end of the added 90 days, the exposure period will end. The definition of exposure might differ between data source and will be further defined in the SAP. Reason for treatment discontinuation will also be collected where available. Exposure of other treatments of interest, that were given prior to the index date, will be defined using a similar methodology that will be detailed in the SAP.

Hemlibra—F. Hoffmann-La Roche Ltd Protocol BO44691, Version 2.0

Register	Country	Start / stop dates	Dosage	Frequency	Reason for treatment*
UKNHD	UK	Captured	Captured	Captured	Captured
FranceCoag	France	Good	Good	Derived	Good
HemoNED	Netherlands	Moderate (start only)	Captured	Captured	Captured
ATHNdataset	US	Good	Good	Good	Good
WBDR	Multi- country	Good	Good	Good	Good
CBDR	Canada	Good	Good	Good	Good

Table 4. Treatment information in each data source.

*Prophylaxis, on demand or other.

UKNHD, UK National Haemophilia Database; **UK**, United Kingdom; **ATHNdataset**, American Thrombosis and Hemostasis Network; **US**; United States; **WBDR**, World Bleeding Disorders Registry; **CBDR**, Canadian Bleeding Disorders Registry.

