8.5.2. Minimum required sample size

To assess whether the real-world estimate obtained in section 8.5.1. will be adequate to investigate the primary study objective of determining the crude IR of 1st TE, a statistical estimation is presented below. A target sample size of ~200 exposed patients with an average follow-up of 4 years for each patient was considered. From simulation runs, this target sample size will ensure 88% probability that the 95% Clopper-Pearson confidence

interval (CI) of the crude IR does not exceed a threshold value of one event per 100 person-years (PY), considering the expected IR of AEs for the primary objective of 0.15 events per 100 PY.

In the emicizumab clinical trial program, a 0.38% incidence risk (3 out of 798 patients) was observed and an IR of 0.15 events per 100 PY with a 95% CI (0.03-0.44) for serious TE events not associated with concomitant aPCC in HA patients. The average duration of exposure was 138 weeks (2.65 years), with a median duration of exposure of 104 weeks (2 years). These findings align with the TE event risk observed in the European Haemophilia Safety Surveillance (EUHASS) registry, which was 0.40% (4 out of 1319 patients).

Table 9 presents alternative scenarios for the estimation's accuracy, defined as the probability that the upper limit of the IR 95% CI does not exceed a certain threshold. This is obtained via calculations with different target sample sizes. For the first alternative scenario, the same expected event rate as above is assumed, and the threshold value for the 95% CI remains as indicated previously. In the second scenario the expected event rate is increased to 0.5 per 100 PY and the threshold value for the 95% CI is changed to 1.5 events per 100 PY.

	Accuracy CI								
Target Sample Size	Expected event rate: 0.15 per 100 PY Threshold: 1 event per 100 PY	Expected event rate: 0.5 per 100 PY Threshold: 1.5 event per 100 PY							
N=175	72%	73%							
N=200	88%	79%							
N=225	95%	83%							

Table 9. Accuracy estimation for different targets of sample sizes, expected event rates and Clopper-Pearson 95% CI threshold values.

CI, Confidence Interval; N, Sample Size; PY, Person Years.

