8.7.2. Planned Analyses

For the analysis of the primary objective and secondary objectives 1, 2, and 3 the overall crude and crude stratified IRs will be calculated. The person-time of each patient will be based on the follow-up and censoring criteria presented in section 8.2.4. and 8.2.5.

For the calculation of crude IRs, the denominator will be the pooled person-time of all the patients within the cohort. The patient time-at-risk will be calculated from index date until the date of an incident event or censoring, whichever occurs first. All first events occurring during follow-up period will be counted in the total number of events. Crude IRs will be presented per 100 PY with 95% CI.

For the primary objective, the numerator will be the number of first TE events of all patients within the cohort. For secondary objectives 1, 2, 3 the numerator will be the number of first occurrences of any SAE; TMA events or serious systemic hypersensitivity reactions, including anaphylaxis; respectively.

For the analysis of secondary objective 4, calculation of crude stratified IRs of 1st TE events will be done. The events will be counted for each category/stratum of relevant pre-defined risk factors (see section 8.3.2.4. for a listing of considered risk factors). More details on the risk factor based tabulations will be presented in SAP.

For analysis of secondary objective 5, characteristics of TE events, SAEs, TMA, and serious systemic hypersensitivity reactions, including anaphylaxis (e.g., diagnosis and symptoms), will be tabulated. In addition, time to 1st TE event; time to 1st TMA event; time to 1st serious systemic hypersensitivity reactions, including anaphylaxis; and time to any 1st SAE event will be described by Kaplan-Meier curves.

For analysis of secondary objective 6, calculation of crude IR and crude incidence proportion of TE, TMA events, SAEs and serious systemic hypersensitivity reactions, **Hemlibra—F. Hoffmann-La Roche Ltd** Protocol BO44691, Version 2.0

including anaphylaxis, will be calculated and tabulated for FVIII prophylaxis use (yes/no) prior to emicizumab treatment.

Patient demographic and clinical characteristics will also be tabulated in relation to the AEs (TE events, SAEs, TMA events and serious systemic hypersensitivity reactions, including anaphylaxis) and in total.

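### The 88% accuracy rests on a rate for serious, non-aPCC TE events, so it is a best case for a primary endpoint that counts any first TE event, and no planned rate isolates non-aPCC TE

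*Protocol*

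**What the plan says.** Three parts of the protocol describe the TE outcome differently.

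- **Commitment.** Section 6.2, and the synopsis in the same terms, says the study was proposed "to characterise the important potential risk of thromboembolic (TE) events (not associated with aPCC exposure) specifically".
- **Primary endpoint.** Section 8.3.1 states: "The primary safety variable is TE events as recorded in the data source". Section 8.7.2 adds that "the numerator will be the number of first TE events of all patients within the cohort". Neither restricts by seriousness or aPCC use. Hypersensitivity reactions, by contrast, are limited to serious ones in section 8.3.1.
- **Planning rate.** Section 8.5.2 takes a rate of 0.15 per 100 PY (95% CI 0.03 to 0.44) from the clinical trial programme, where it was observed "for serious TE events not associated with concomitant aPCC in HA patients". In the synopsis (Study Size) the same 0.15 appears simply as the expected crude rate of TE events.

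On aPCC, section 8.2.6.2 excludes patients with a noted inhibitor or any bypassing agent before the index date. aPCC use during follow-up is not a censoring reason (8.2.5), a candidate TE risk factor (8.3.2.4), a named subgroup (8.7.3) or one of the four sensitivity analyses (8.7.4, Table 10). Section 8.3.2.2 says of data availability: "All registers cover the haemophilia related treatments: emicizumab, aPCC, Eptacog alfa (activated), and Factor VIII transfusions".

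In Table 9 the only scenario with a higher rate changes two inputs together: "the expected event rate is increased to 0.5 per 100 PY and the threshold value for the 95% CI is changed to 1.5".

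**The concern.** The accuracy statement is the protocol's argument that about 200 patients suffice for the primary objective. It was calculated with the rate of a subset of the events that will be counted. Only about 1.2 events are expected and at most 2 are tolerated, so one or two non-serious or aPCC-associated events could decide whether the upper limit stays below 1 per 100 PY. Table 9 does not show this sensitivity, because its higher-rate column also relaxes the threshold.

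Separately, the headline rate mixes aPCC-associated events, if any occur, with the risk the commitment names, and no planned rate separates them.

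**Working it through.** **Inputs (section 8.5.2).** N=200; average follow-up 4 years; rate 0.15 per 100 PY; threshold 1 per 100 PY; two-sided 95% Clopper-Pearson interval.

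**Step 1: events tolerated.** Person-time is 200 × 4 = 800 PY, treated as 800 trials. The upper limit for x events is the 97.5th percentile of Beta(x+1, 800−x).

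- x=2: 0.900 per 100 PY, within the threshold.
- x=3: 1.092 per 100 PY, above it.

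The target is met with at most 2 first events.

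**Step 2: the plan's own figure.** The expected count is 800 × 0.0015 = 1.2. In the Poisson form, P(X≤2) = e^(−1.2) × (1 + 1.2 + 1.2²/2) = 0.3012 × 2.92 = 0.8795; the exact binomial gives 0.8796. The stated 88% reproduces. So do the other Table 9 cells:

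| N | Rate 0.15, threshold 1: stated / recomputed | Rate 0.5, threshold 1.5: stated / recomputed |
|---|---|---|
| 175 | 72% / 71.7% | 73% / 72.6% |
| 200 | 88% / 88.0% | 79% / 78.5% (exact 0.7855) |
| 225 | 95% / 95.2% | 83% / 83.2% (exact 0.8315) |

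The arithmetic of the plan is right.

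**Step 3: the same calculation at other rates, N=200, threshold kept at 1.** The protocol gives no person-time rate for all recorded TE events, so rates above 0.15 are assumptions.

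| Rate per 100 PY | Expected events | P(X≤2) | Origin of the rate |
|---|---|---|---|
| 0.15 | 1.2 | 88.0% | serious non-aPCC TE, trial programme |
| 0.20 | 1.6 | 78.4% | assumed |
| 0.25 | 2.0 | 67.7% | assumed |
| 0.30 | 2.4 | 57.0% | assumed (twice the planning rate) |
| 0.44 | 3.52 | 31.7% | upper limit of the planning rate's own CI |
| 0.50 | 4.0 | 23.7% | Table 9's second rate |

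At 0.50, Table 9 shows 79% because the threshold moved to 1.5, which allows 5 events (upper limit 1.452) instead of 2.

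**Step 4: direction.** Serious non-aPCC TE events are a subset of all TE events. In the same patients, with the same recording, the rate of the broader endpoint is equal or higher. If 0.15 is right for the subset, 88% is therefore the most that N=200 can offer for the planned primary endpoint.

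**The case against.** The strongest points on the other side are these.

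- **aPCC is largely handled at entry.** Only a patient who develops an inhibitor on treatment, or otherwise receives aPCC after index, can contribute an aPCC-associated event. This stands: that part of the shift is probably small. A reader might infer that the primary estimate cannot answer the question behind the commitment; the documents do not support that. The seriousness restriction may matter more.
- **Events are described individually.** Section 8.3.2.1 plans detail on hospitalisation and additional haemophilia treatments where available, and secondary objective 5 tabulates event characteristics. With so few events, an aPCC-associated case could often be recognised. That helps, but it is no planned rate.
- **Section 8.5.2 also cites a EUHASS TE risk that carries no such restriction.** It is 4 of 1319 patients, printed as 0.40% although 4/1319 = 0.30%. Either value is near the trial programme's 0.38%. This stands as evidence that the broader endpoint need not be much more frequent, but without person-time it gives no rate.
- **The higher rates do not measure the mismatch.** This stands. The 0.44 reflects sampling uncertainty in the narrow rate, and the other values are assumed or borrowed.
- **N may exceed 200.** Table 8 projects 202 to 540 patients. By the same method at 0.30, N=324, 338 and 540 give 80%, 88% and 98%. The stated 88% is nevertheless for 200.
- **The study is descriptive (8.7.1), and counting all TE events is a defensible, inclusive safety choice.** This stands. A reader might infer that the primary endpoint must be replaced by non-aPCC TE. That does not follow, because such an endpoint would still not match a rate limited to serious events.
- **Operational detail belongs in the SAP.** True of event mapping, but the protocol itself fixes the primary variable, the numerator and the planning rate, and these disagree.

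**Conclusion.** The mismatch is in the text. The 88% is computed correctly but describes serious, non-aPCC TE events; for the planned endpoint it is a best case at N=200. The loss is of unknown size: about 10 percentage points if the all-TE rate were 0.20 per 100 PY, and about 31 if it were 0.30. Neither rate is predicted by the documents. This assumes 800 PY are reached, 0.15 holds for the narrow endpoint in this population, and registries record TE as completely as the trial programme did.

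Two further points hold whatever the true rate. Table 9 does not show how accuracy falls at the planned threshold, and no planned rate isolates the non-aPCC TE risk named in sections 3 and 6.2. The primary endpoint itself can stay as it is.

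**What to change.** 1. Keep the first TE event of any kind as the primary numerator.
2. In section 8.7.2, add a prespecified supporting crude rate with 95% CI for first TE events not associated with concomitant aPCC and, where seriousness is recorded, one for serious non-aPCC TE events. The SAP should define association with aPCC and say how undated or missing aPCC records are handled; the protocol says that registers cover aPCC, not that dates are adequate for event-level attribution.
3. In the synopsis (Study Size) and section 8.5.2, state that 0.15 per 100 PY and 88% refer to serious TE events not associated with aPCC.
4. Add to Table 9, for N=200 and the unchanged threshold of 1 per 100 PY, the rates 0.20, 0.30, 0.44 and 0.50 (about 78%, 57%, 32% and 24%). Label them as assumed and identify 0.44 as the upper limit of the planning rate's interval.

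The cost is protocol and SAP wording, slightly more tabulation and a less favourable stated accuracy. No new data collection is evident, since aPCC is said to be covered by every register.
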